4.10 Efficacy Analysis

Analysis of the efficacy endpoints for the Interim Analysis will be limited to data collected during the double-blind period. Open-Label efficacy data will be included in the listings only. Following the Interim Analysis, additional analyses including open-label efficacy data will be described in a later version of the SAP, for presentation as part of the Final Analysis.

4.10.1 Primary Efficacy Endpoint

The PKAN-ADL consists of 12 items related to activities of daily living, including eating, dressing, and walking. Each item has responses ranging from 0-4, with a higher value indicating greater disability in the given activity. To compute the total score, responses are summed across the 12 items.

For analysis purposes, data from the pediatric and adult age groups will be pooled. All descriptive summary tables will be repeated using age group as a subgroup.

Descriptive statistics will be presented for the PKAN-ADL total score, with absolute and percent change from baseline, by treatment group for each visit of the double-blind

period. For post-baseline assessments, categories for change from baseline total score (e.g., >0 , $=0$, <0 , ≤ -1 , ≤ -2 , ≤ -3 , ≤ -4), categories for percent improvement (i.e., decrease) in total score from baseline (i.e., $<0\%$, $=0\%$, $>0\%$, $\geq 10\%$, $\geq 20\%$, $\geq 30\%$, $\geq 40\%$, $\geq 50\%$), and categories for total score status (improvement, no change, or worsening) will be presented. These categories may be adjusted in a way that ensures that the categories contain at least 10% of patients. This will be run using the Double-Blind FAS, and repeated using the PPS, as a sensitivity analysis.

Change from baseline will be calculated by subtracting the baseline total score from the post baseline total score. Percent change from baseline will be calculated as:

$$100 * (\text{Observed Score at Post-Baseline Visit} - \text{Observed Score at Baseline}) / \text{Observed Score at Baseline}$$

Furthermore, a chi-squared test will be performed at each post-baseline visit to determine treatment differences between the percentages of patients who had a total score indicating improvement, no change, or worsening. Proportions, with estimated 95% CI, will be reported for each treatment group, along with a p-value corresponding to the treatment comparison.

Frequency tables will display change from baseline for each of the 12 items, as well as shift from baseline, by treatment group for each post-baseline assessment of the double-blind period. In addition, categories for change from baseline item score (i.e., >0 , $=0$, <0 , ≤ -1 , ≤ -2 , ≤ -3), and categories for item score status (improvement, no change, or worsening) will be presented. These summaries will be run using the Double-Blind FAS and repeated using the PPS, as a sensitivity analysis.

Figures will be presented which show the PKAN-ADL total score for each visit during the double-blind period, as well as change from baseline score, by treatment group. This will be run using the Double-Blind FAS and repeated using the PPS.

In addition, a by-patient listing will be provided, which presents PKAN-ADL scores (total and for each item) across all assessments in the double-blind and open-label periods for patients in the Double-Blind FAS.

The change from baseline in PKAN-ADL total scores will be used to test the following hypotheses:

Null hypothesis:

There is no difference between the fosmetpantotenate and placebo groups, as measured by the change in PKAN-ADL total score from baseline to the end of the 24-week double-blind treatment period, with adjustment for age group and baseline PKAN-ADL total score.

Alternate hypothesis:

There is a difference between the fosmetpantotenate and placebo groups, as measured by the change in PKAN-ADL total score from baseline to the end of the 24 week double-blind treatment period, with adjustment for age group and baseline PKAN-ADL total score.

That is:

H_0 : Change from baseline PKAN-ADL Total Score at Week 24 (fosmetpantotenate) = Change from baseline PKAN-ADL Total Score at Week 24 (Placebo) *estimated via repeated measure analysis, with adjustment for age group and baseline score*

H_1 : Change from baseline PKAN-ADL Total Score at Week 24 (fosmetpantotenate) \neq Change from baseline PKAN-ADL Total Score at Week 24 (Placebo) *estimated via repeated measure analysis, with adjustment for age group and baseline score*

The primary efficacy analysis will be based on the FAS population in the double-blind period of the study. For each patient, the change from baseline in PKAN-ADL total scores at Weeks 3, 6, 12, 18, and 24 of the double-blind period will be used for analysis. The treatment effect will be evaluated on the basis of a mixed model for repeated measures (MMRM) analysis to assess data from all visits simultaneously. The model will include fixed effects for treatment, age group (pediatric, adult), visit and treatment by-visit interaction, with visit as the repeating factor and patient as a random effect, and baseline PKAN-ADL total score as a covariate. The PKAN-ADL total score obtained prior to the first dose of investigational product will serve as each patient's baseline value.

Patients with PKAN-ADL administration errors will be included in the Double-Blind FAS, but excluded from the PPS, as per [Section 4.5](#). Imputation rules for the data affected by the translation issue can be found in [Section 4.1](#).

The linear mixed-effect model will be implemented using PROC MIXED in SAS with the restricted maximum likelihood (REML) estimation method. An unstructured variance-covariance matrix will be used to model the within-patient errors. [Note: In the unlikely event that the computational algorithm fails to converge, the following structures will be executed in the order specified (essentially in decreasing order of complexity) until convergence is achieved: Toeplitz with heterogeneity, autoregressive with heterogeneity by Week, compound symmetry with heterogeneous variances by Week, autoregressive, Toeplitz, and compound symmetry without heterogeneous variances by Week.]

Significance tests will be based on least squares means (LSMs) using Type III sum of squares. The Kenward and Roger method will be used for calculating the denominator degrees of freedom for tests of fixed effects.

The PROC MIXED SAS coding is as follows:

```
proc mixed data=DATA;
    class TRT WEEK PATIENT;
    model C_score = BASE_score AGE TRT WEEK TRT*WEEK / solution
    ddfm=kr;
    repeated WEEK / subject=PATIENT type=un;

run;

where:
    TRT = treatment group (0 = placebo, 1 = fosmetpantotenate)
    WEEK = week 3, 6, 12, 18, 24
    AGE = age group (0=Pediatric, 1= Adult)
    C_score = change in score from baseline
    BASE_score = baseline score
```

The LSMS for each treatment, the difference between the LSMSs, and the standard error (SE) and 95% confidence interval (CI) associated with the difference will be reported at each study visit. The primary treatment comparison will be based on the test of contrast between treatment effects using the LSM estimate at Week 24, adjusted for baseline score and age group from the Type III analysis.

To estimate the mean change from baseline for PKAN-ADL total scores in each treatment group (placebo or fosmetpantotenate) at Week i ($i = 3, 6, 12, 18$, and 24), the following estimate statement (as an example) will be utilized:

```
estimate 'Placebo Group at Week 24'
    intercept 1
    AGE        <proportion in age group=0  proportion in age group=1>
    BASE_score <mean of BASE_score>
    TRT        1 0
    WEEK       0 0 0 0 1
    TRT*WEEK   0 0 0 0 1
                0 0 0 0 0 / cl;
estimate 'FOSMETPANTOTENATE Group at Week 24'
    intercept 1
    Age        <proportion in age group=0  proportion in age group=1>
    BASE_score <mean of BASE_score>
    TRT        0 1
    WEEK       0 0 0 0 1
    TRT*WEEK   0 0 0 0 0
                0 0 0 0 1 / cl;
```

To estimate the treatment effect (i.e., the difference between fosmetpantotenate and placebo) at Week i ($i = 3, 6, 8, 12$, and 24), the following estimate statement (as an

example) will be utilized:

```
estimate 'Treatment Effect at Week 24'  
    TRT      -1 1  
    TRT*WEEK  0 0 0 0 -1  
              0 0 0 0 1 / cl;
```

The point estimates and corresponding 95% CIs for the treatment effect at each week will be presented for the FAS (double-blind period).

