12.9. Efficacy

12.9.1. Double-Blind Period

The primary efficacy analysis will be based on the FAS population defined for the double-blind period of the study (see [Section 12.3](#)). For each patient, the change from Baseline in PKAN-ADL scores at Weeks 3, 6, 12, 18, and 24 of the double-blind period will be used for analysis. The treatment effect will be evaluated on the basis of mixed model for repeated measures (MMRM) analysis to assess data from all visits simultaneously. The model will include fixed effects for treatment, age stratum (6 to <18 or 18 to 65 years), visit and treatment by-visit interaction, a random effect for patient within treatment group, and Baseline

PKAN-ADL score as a covariate. The PKAN-ADL measurement obtained prior to the first dose of investigational product will serve as each patient's Baseline value. Least-squares adjusted means and the adjusted mean difference between treatment groups will be reported at each study visit, along with 2-sided 95% confidence intervals (CIs) and the p-value for the treatment comparison.

The mixed-effect linear model will be implemented using PROC MIXED in SAS with the restricted maximum likelihood (REML) estimation method and Kenward-Roger degrees of freedom algorithm for the F-test. Significance tests will be based on least squares means using Type III sum of squares.

To support the primary efficacy analysis, analysis of covariance (ANCOVA) models will be applied to change from Baseline in PKAN-ADL scores assessed after 3, 6, 12, 18, and 24 weeks of treatment. For each week analyzed, the model will include treatment and age stratum (6 to <18 or 18 to 65 years) as fixed effects and Baseline PKAN-ADL score as a covariate. Estimates of the adjusted mean treatment differences and the 2-sided 95% CIs at each time point will be obtained from the model.

Secondary and exploratory efficacy endpoints that are continuous measures recorded at each study visit will be evaluated using the MMRM approach described above for the primary efficacy endpoint. Summary statistics for efficacy measures will include graphical plots of mean and mean change from Baseline values at each study visit, by treatment group.

Treatment effects on categorical outcomes will be examined using frequency tables and tested using Cochran-Mantel-Haenszel chi-square methods with stratification by age group (6 to <18 or 18 to 65 years).

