4.2 Determination of Sample Size

It is estimated that a total of 74 patients (37 in each treatment group) will provide approximately 80% power to detect a 3-point difference between groups in the average change from baseline score for the PKAN-ADL, based on Student's t-test with alpha=0.05 (two-sided); this calculation assumes a standard deviation of 4.5 points for the change from baseline scores. Allowing for 10% attrition, a total of 82 patients will be randomized to achieve the target sample size of at least 74 patients completing the double-blind period of the study.

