4.10.3 Exploratory Efficacy Endpoints

Exploratory efficacy endpoints that are continuous rating scales recorded at multiple post-baseline visits (i.e., BAD Scale, Neuro-QOL, Euro-QOL, 25-foot walk test) will be evaluated using the MMRM approach described above for the primary efficacy endpoint. For endpoints obtained only at the baseline and final (Week 24) visits of the double-blind period (i.e., FIM/WeeFIM, DDK), the ANCOVA model will be used. The model will be run using the observed case (OC) procedure only. Summary statistics for efficacy measures will include graphical plots of mean and mean change from baseline values at each study visit during the double-blind period, by treatment group.

For analysis purposes, data from the pediatric and adult age groups will be pooled. All descriptive summary tables will be repeated using age group as a subgroup.

Treatment effects on categorical outcomes will be examined using frequency tables and tested using the Cochran-Mantel-Haenszel (CMH) chi-square methods with stratification by age group (pediatric, adult) ([Mantel and Haenszel, 1959](#)).

For the Interim Analysis, the Double-Blind FAS only will be used for analyses involving exploratory efficacy endpoints.

Statistical methods and estimation procedures are described below for each of the exploratory endpoints.

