4.10.3.1 Clinician Global Impression of Improvement (CGI-I)

The CGI-I is measured on a 7-point scale, ranging from 1=very much improved to 7=very much worse since the start of treatment. Frequency tables will display the distribution of CGI ratings in each treatment group at Weeks 3, 6, 12, 18, and 24 of the double-blind treatment period. In addition, the percentages of patients who had a score indicating improvement, no change, or worsening, will be presented. This will be repeated using age group (pediatric, adult) as a subgroup.

The Cochran-Mantel-Haenszel test (CMH) row-mean score test (van Elteren test) will be used to evaluate the difference between treatment groups in average CGI-I ratings at each visit during the double-blind period, with stratification by age group (pediatric, adult).

A chi-squared test will be performed at Week 24 to determine treatment differences between the percentages of patients who had a score indicating improvement, no change, or worsening. Proportions, with estimated 95% CI, will be reported for each treatment group, along with a p-value corresponding to the treatment comparison.

A by-patient listing will be provided, which presents CGI-I scores across all assessments in the double-blind and open-label periods for patients in the Double-Blind FAS.

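### The improvement/no change/worsening comparisons use a plain chi-squared test that ignores category order and omits the age stratification that the plan's own rule for categorical outcomes calls for

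*SAP*

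**What the plan says.** - **PKAN-ADL (SAP 4.10.1).** Each patient's total score is classed as improved, unchanged or worse, and "a chi-squared test will be performed at each post-baseline visit to determine treatment differences between the percentages of patients" in these classes. Per-arm proportions with 95% CIs and a p-value are reported.
- **UPDRS Part III (SAP 4.10.2).** The same test at each post-baseline visit.
- **Exploratory scales.** The same test for BAD (4.10.3.2), Neuro-QoL by module (4.10.3.3.1), EQ-5D index (4.10.3.3.2) and FIM/WeeFIM (4.10.3.4). For CGI-I (4.10.3.1): "A chi-squared test will be performed at Week 24 to determine treatment differences between the percentages of patients" in the three classes. None is planned for the walk test or the speech assessments.
- **Protocol 12.9.1.** Categorical outcomes are to be tested by "Cochran-Mantel-Haenszel chi-square methods with stratification by age group". The protocol synopsis says only that chi-square methods will be used.
- **SAP 4.10.3**, for the exploratory endpoints, says categorical outcomes are "tested using the Cochran-Mantel-Haenszel (CMH) chi-square methods with stratification by age group (pediatric, adult").
- **CGI-I on the full 7-point rating (SAP 4.10.3.1).** A CMH row-mean-score (van Elteren) test stratified by age group.
- **SAP 4.10.4.** Only the primary and secondary endpoints are in the gate-keeping sequence; the rest is exploratory.

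**The concern.** Improved, unchanged and worse form an ordered outcome. A chi-squared test on three percentages, with no scores named, is by default the Pearson test on 2 degrees of freedom. It asks whether the two distributions differ in any way, so it spends a degree of freedom on differences with no clinical direction. It also leaves out age group, which is a randomisation stratum and a term in the primary model.

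Two things follow. When patients really do shift towards improvement, the test is less likely to show it than an ordered test. And a small p-value need not mean benefit: an arm with more improvers and equally more worseners can produce one. What is at stake is how the supporting p-values on the primary and secondary scales are read. There is also a practical problem: for the exploratory scales, the general rule in SAP 4.10.3 and the endpoint paragraphs give a programmer different instructions on stratification.

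**Working it through.** **Inputs.** From SAP 4.2: "a total of 74 patients (37 in each treatment group) will provide approximately 80% power to detect a 3-point difference between groups", and "this calculation assumes a standard deviation of 4.5 points for the change from baseline scores". Category rates, placebo mean change, age effect and age split are not given in the documents and are assumed below.

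**The plan's own figure.** Standard error of the difference = 4.5 × √(2/37) = 1.046; 3/1.046 = 2.867. Normal approximation: Φ(2.867 − 1.960) = 81.8%. Noncentral t with 72 df: 80.8%. The stated 80% reproduces.

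**Category rates implied by that scenario.** Assume roughly normal changes rounded to whole points, so that unchanged means between −0.5 and +0.5.

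| Arm | Improved | Unchanged | Worse |
|---|---|---|---|
| Placebo, mean 0 | 45.6% | 8.8% | 45.6% |
| Active, mean −3 | 71.1% | 7.1% | 21.8% |

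**Power at 37 per arm (simulation, at least 8,000 runs per scenario).**

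| Scenario | Pearson, 2 df | Row-mean score, 1 df |
|---|---|---|
| 3-point shift, unstratified | 53% | 64% |
| Placebo mean change varied from −1 to +2, unstratified | 50–55% | 60–65% |
| Age effect of ±2 points, row-mean stratified by age | 43–45% | 59–61% |

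The last row uses assumed age splits of 11/26 and 18/19 per arm. With identical arms both tests reject in about 5% of runs.

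**A clear shift, one table.** Improved/unchanged/worse 17/11/9 against 9/11/17. Expected counts are 13/11/13 per arm, so Pearson = 4 × 16/13 = 4.92, p = 0.085. Row-mean: the summed score in the first arm is +8 against 0 expected, with variance (37 × 37/73) × (52/74) = 13.18; 64/13.18 = 4.86, p = 0.028.

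**No net benefit, one table.** 7/23/7 against 15/7/15. Expected counts are 11/15/11 per arm, so Pearson = 4 × 16/11 + 2 × 64/15 = 14.35, p = 0.0008. Improved minus worse is 0 in both arms, so row-mean p = 1.0.

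**How likely is that on PKAN-ADL?** With zero mean change in both arms, only a difference in spread can alter the unchanged share. Rejection by Pearson in 20,000 runs:

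| SDs of the two arms | Unchanged | Pearson rejects |
|---|---|---|
| 4.5 and 6 | 8.8% and 6.6% | about 5% |
| 4.5 and 9 | 8.8% and 4.4% | about 7% |
| 3 and 6 | 13.2% and 6.6% | about 11% |
| 2 and 4.5 | 19.7% and 8.8% | about 20% |

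The row-mean test stays near 5% throughout.

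**Would stratification alone be enough?** No. With assumed rates of 40.5/19/40.5% against 27/46/27%, the age-stratified CMH general-association test still rejects in 60–61% of runs, against about 5% for the stratified row-mean test. The replacement must name both the strata and the statistic.

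**The case against.** The strongest defence is that little depends on these tests, and that is right. Four stronger readings are tempting, and the documents do not support them.

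- *These are the only between-arm tests of the direction of change.* They are not. The mixed model reports a signed difference with its CI at each visit for PKAN-ADL and UPDRS Part III, and ANCOVA with observed cases and LOCF repeats it. All adjust for age group. The chi-squared test is only the planned test of the three-class status.
- *The test will usually be significant without benefit.* If 60% of one arm and 20% of the other were unchanged, with improvers and worseners balanced, it would reject in about 91% of trials. Under the normal model used here, those shares imply SDs near 0.6 and 2.0, whereas SD 4.5 gives about 9% unchanged. A spike at zero, a wider no-change band or a coarse scale such as CGI-I could bring the effect back, but the documents give no such rates.
- *The SAP breaks a protocol requirement for an ordered test.* Neither document requires one. The departure from protocol 12.9.1 concerns stratification only, and the synopsis wording would permit an unstratified test.
- *Type I error control is damaged.* The gate in SAP 4.10.4 is untouched.

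It can also be said that SAP 4.10.3 governs only the exploratory scales, that its endpoint paragraphs may be meant to override the general rule, that the status classes for PKAN-ADL and UPDRS Part III are summaries added by the SAP, and that the per-arm percentages would reveal a symmetric spread. These points lower the stakes. They do not explain why CGI-I gets an ordered, age-stratified test on seven categories and then loses both features when collapsed to three. The SAP cites Protocol Version 3.0, and the supplied protocol was approved after the SAP was signed; because SAP 4.10.3 carries the same rule, the inconsistency within the SAP does not depend on the protocol version.

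**Conclusion.** The point holds as a cheap improvement to supportive and exploratory analyses. The chi-squared test is at odds with the age-stratified rule in protocol 12.9.1, and with SAP 4.10.3 for the exploratory scales. It also costs about 10 percentage points of power under the plan's own effect: 53% against 64%, given roughly normal changes, a cut at zero change and placebo mean change 0. The further loss from ignoring age depends on an assumed age effect. Significance without net benefit is a real property of the test, but for PKAN-ADL near the assumed SD it is slight: about 5–8% rejection for SDs of 4.5 against 6 to 9, rising to about 20% for 2 against 4.5. That the test is unordered is inferred from the wording, since no statistic or degrees of freedom are named. The primary and secondary conclusions are not affected.

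**What to change.** In SAP 4.10.1, 4.10.2, 4.10.3.1 to 4.10.3.3 and 4.10.3.4, replace the chi-squared test on the three classes by the CMH row-mean-score test stratified by age group, with scores -1, 0, 1 stated explicitly and ordered from worse to improved, so that the direction is the same on every scale. Keep the per-arm percentages and 95% CIs. For CGI-I this supplements the stratified row-mean-score test already planned on the 7-point ratings.

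The cost is SAP wording and a small change to the PROC FREQ call; no new data are needed. The one downside is that the test is insensitive to a pure difference in spread between arms, which stays visible in the reported percentages.
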